6.1.2 Infusion of the Investigational Product

Infusion of AAT will start on the day of islet transplantation before anesthesia and pancreatectomy, which is approximately 6-8 hours before islet infusion. The clinical PIs, Drs. [name] and [name], will identify the time to start the study drug infusion. Starting and ending time of drug administration, amount of drug infused, and infusion rate will be recorded for each subject. On Average, TP-IAT patients stay in the hospital for 7-28 days after islet transplantation. If they stay till 21 days post transplantation, they can have all four AAT injections in the hospital. If they are discharged earlier, patients will be requested to return to MUSC for additional drug infusion(s). A nurse will administer the AAT or placebo infusion to the patient while in the hospital. A nurse in the GI surgery clinic or SCTR outpatient clinic will administer AAT or placebo to patients discharged but returning for one of the weekly visits. The nurses infusing these drugs will be trained on the day of administration concerning the few known side effects of AAT and rate of infusion.

6.2. DRUG ADMINISTRATION POST HOSPITAL STAY

In the case when patient is discharged before completion of 4 doses of AAT, they will be asked to return to MUSC at the required times to get the investigational drug administered. Starting and ending time of drug administration and the infusion rate will be recorded for each drug administration. Serum AAT level will be measured before and 30 mins after the first drug administration.

6.3. POST-OPERATIVE ASSESSMENTS

All routine measurements for TP-IAT patients will be measured according to current protocols for this patient population. SF-12 Quality of life and reduction in narcotic dose of morphine or equivalent will be obtained from the Islet Longitudinal Outcome Database (ILOD) which has granted this project authorization to use their information. . The following will be assessed during hospital stay and each time or when patients return for drug injection:

6.3.1. Instant blood mediated inflammatory reaction (IBMIR): 3ml of blood will be collected before AAT injection, before, in the middle, and after initiation of islet infusion and 3h post islet infusion. Serum will be collected and stored in -70 ° C for analysis of thrombin-anti-thrombin complex (TAT), C5a, and c-peptide level.

6.3.2. Chemokines/cytokines: A blood sample will be obtained at 0, 24, 72, and 168 h (before AAT injection), and day 14 (before AAT injection), and 21 (before AAT injection) post transplantation to measure chemokine and cytokine expression in the serum using the Lumix machine. Each time 5 ml of blood will be collected and centrifuged; aliquots of serum will be stored in in -70 ° C for further analysis.

6.3.3. DNA testing: A 10 ml whole blood sample will be collected during screening, and stored in -70 °C for isolation of genomic DNA for further analysis. This future analysis may be conducted by the PI or by other researchers who obtain IRB approval for their research. This research may involve genetic studies. The specimens will be labeled with a code that only study personnel can link back to the patient. Researchers outside of this study will not be given a link between the code number and patient's name or any other identifying information. We expect to store the specimens long-term for future studies on disease condition. Participant will not be contacted for additional consent. The investigators will not tell patient what they find out about the patient, nor will contact the patient if a test becomes available to diagnose a condition that a patient might have or later develop. Results will not be placed in the individual participant's medical record.

There is a risk of potential loss of patient's privacy or confidentiality. Information about race, ethnicity, sex, medical history, and so forth might be available to investigators studying the specimen. Such information might be important for research or public health. It is possible that this information (including genetic information) might come to be associated with patient's racial or ethnic group. The specimens obtained from patients in this research may help in the development of a future commercial product. There are no plans to provide financial compensation to patient should this occur. Whether patient will agree to have their blood stored will not impact their participation in the study.

6.3.4. RNA and other analyses: PBMCs (10ml blood) and plasma (15ml of blood) will be collected at 168 h post transplantation and stored in -70 °C for RNA expression, proteomics, metabolics and small RNA analysis.

6.3.5. The total amount of blood drawn for research purposes will be 145 ml (10 tablespoons) over the course of the study.

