2.1.2. Alpha-1 antitrypsin (AAT)

AAT is a serine protease inhibitor that belongs to the serpin family. It has a high concentration in serum, and is available for clinical use as an affinity-purified human product (2). AAT inhibits various enzymes including neutrophil elastase, cathepsin G, proteinase-3, thrombin, trypsin, and chymotrypsin (3). Patients with a genetic deficiency in AAT exhibit 15-60% lower circulating AAT levels than normal and are prone to develop pulmonary emphysema (4). Besides inhibition of neutrophil elastase, AAT exerts anti-inflammatory effects via suppressing cytokine production, complement activation, and immune cell infiltration. AAT also functions as an anti-apoptotic factor for endothelial cells and vascular smooth muscle cells (5,6). AAT induces vascular endothelial growth factor (VEGF) expression and release, protects VEGF from proteolytic cleavage by elastase, promotes viability of endothelial cells, and enhances migration of myocytes. Recent studies indicated that AAT had profound beneficial effects in the treatment of diabetes. AAT protects β cells from apoptosis induced by pro-inflammatory cytokines and streptozotocin (7). A single injection of AAT to NOD mice reduced the intensity of insulitis, increased β cell mass, promoted β cell regeneration, and prevented the onset of diabetes via modulating T regulatory cells (8,9). AAT has been shown to protect islets from graft failure and immune rejection in mouse transplantation models with readily vascularized islet grafts (10,11). Adding AAT into ductal injection solution and collagenase solution improved porcine islet isolation by inhibiting trypsin activity during pancreas digestion (12). AAT monotherapy

elevates VEGF expression levels in islet allograft and prolongs islet allograft survival in mice via enhancement of intraislet VEGF expression and promotion of islet revascularization (11).

A recent study published by Koulmada and colleagues demonstrated that AAT treatment improved survival of islets after partial pancreatectomy and intrahepatic autologous islet transplantation in non-human primates (13). Thus, the beneficial effects of AAT in the islet transplantation setting may be mediated by its anti-apoptotic and anti-inflammatory properties and promotion of islet revascularization.

2.1.3. Clinical trials use of AAT for diseases:

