3.5.3. Exploratory endpoints

- Measurements of primary and secondary endpoints at day 75±14.
- Time course of instant blood mediated inflammatory reaction as measured by thrombin-anti-thrombin (TAT), C5a and c-peptide levels before, in the middle and after initiation of islet infusion, and 3h post islet infusion.
- Time course of inflammatory chemokines/cytokines as assessed by serum level of CXCL8, CCL2 (MCP-1), CCL3, CCL4, CXCL10 (IP-10), CXCL9 (MIG), IL-6, IL-10, INF- γ , TNF- α , and IL-1 β [pre-infusion, and 24, 72 and 168hrs, and day 14, and 21 after the end of islet infusion].
- Basal to 240 min time course of glucose, and C-peptide derived from the MMTT (day 75±14 to day 365±14).
- The proportion of patients with an HbA1c \leq 6.5% (day 365±14 days post-transplant only)
- Cumulative number of severe hypoglycemia events.
- The proportion of patients with an HbA1c \leq 6.5% at day 365±14 AND are free of severe hypoglycemic events from day 75±14 to day 365±14 inclusive.
- Daily oral Morphine Equivalents on day prior to visit (day 75±14 to day 365±14).
- Proportion of patients remaining on narcotics (day 75±14 to day 365±14).
- RNA expression profile in peripheral blood mononuclear cells (PBMCs) at 168 h post transplantation. RNA analysis will be done in at least 10 patients to guarantee post-treatment sampling in at least 3-4 patients randomized to AAT and 3-4 to control.
- SF-12 Quality of Life score

3.5.4. Safety endpoints:

- Incidence and severity of Adverse Events and Serious Adverse Events
- Standard laboratory tests including hematology (hematocrit, hemoglobin, red blood cells, platelets, white blood cells, differential white blood cell count), clinical chemistry (sodium, potassium, serum creatinine, blood urea nitrogen, total bilirubin, alanine aminotransferase (ALT), aspartate aminotransferase (AST) and coagulation (International Normalized Ratio (INR), partial thromboplastin time (PTT)), at pre-transplant hospital admission and post-transplant hospital

discharge].

- Vital signs, i.e. blood pressure (BP) and heart rate (HR) at pre-transplant hospital admission and post-transplant hospital discharge. ALT/AST, INR/PTT
- Weight loss from pre-transplant value [time frame: day 75±14 and 365±14 after the transplant]
- Serum level of albumin and pre-albumin (absolute and change from pre-transplant value) [time frame: day 75±14 and 365±14 after the transplant].

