APPENDIX 1:

Study Phase	Screening	Treatment									Premature Withdrawal
Time points (days relative to transplant)	Screening	Baseline Before Surgery	Baseline After/ During Surgery	Day 1	Day 3	D7	D14	D21	D75	D365	
Visit#	1	2				3	4	5	6	7	
Visit Windows (days)						±2	±2	±2	±15	±15	
Informed Consent	x										
Medical and Diabetes History	x					x	x	x	x	x	x
Inclusion/Exclusion	x										
Immunoglobulin A (IgA)	x										
AAT infusion		x				x	x	x			
TP-IAT			x								
Inflammatory Cytokine Levels		x	x ³	x	x	x	x	x			
TAT, C3a, c-pep	x	x ¹ , x ²									
Serum AAT level		x ⁴									
Blood mononuclear RNA		x				x					
Blood DNA		x									
Plasma for proteomics, siRNA, etc		x				x					
MMTT -240min c-peptide and glucose									x	x	
Adverse Event Recording		x	x	x	x	x	x	x	x	x	x

- 1 Time 0 and 15 minutes after initiation of islet cell infusion in radiology suite.
- 2 Time 3 hours after initiation of islet cell infusion when participant is back in ICU.
- 3 Cytokine profile obtained 24 hours after initiation of islet cell infusion when participant is back in ICU.
- 4 AAT levels will be measured prior and 30mins after the first AAT infusion.

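### Section 6.3.1 specifies serum for TAT, so in-tube clotting is mixed with the patient's own reaction and the marker cannot reliably show IBMIR during islet infusion

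*Combined protocol and SAP*

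**What the plan says.** Section 3.5.3 lists an exploratory endpoint: "Time course of instant blood mediated inflammatory reaction as measured by thrombin-anti-thrombin (TAT), C5a and c-peptide levels". Section 6.3.1 gives the draws: "3ml of blood will be collected before AAT injection, before, in the middle, and after initiation of islet infusion and 3h post islet infusion". It then names the specimen for all three analytes: "Serum will be collected and stored in -70 ° C for analysis of thrombin-anti-thrombin complex (TAT), C5a, and c-peptide level".

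Neither document section nor schedule gives an anticoagulant, a tube type or a time to centrifugation for these draws. Plasma appears as a specimen in its own right elsewhere. Section 6.3.4 states that "PBMCs (10ml blood) and plasma (15ml of blood) will be collected at 168 h post transplantation", for RNA, proteomic and similar work, and Appendix 1 gives that plasma its own row.

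On the drug's action, section 2.1.2 states that "AAT inhibits various enzymes including neutrophil elastase, cathepsin G, proteinase-3, thrombin, trypsin, and chymotrypsin", and that "AAT exerts anti-inflammatory effects via suppressing cytokine production, complement activation, and immune cell infiltration".

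Appendix 1 names C3a, not C5a, in the row for these markers. Its footnotes time the samples at "Time 0 and 15 minutes after initiation of islet cell infusion in radiology suite" and at three hours counted from the start of the infusion.

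**The concern.** TAT is measured here to show how much thrombin forms in the patient when islets enter the portal circulation. A specimen that is itself made by clotting adds thrombin-antithrombin complex after the blood has left the patient. The assay cannot tell the two sources apart.

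Two consequences follow. If in-tube formation varies from tube to tube regardless of arm, it adds noise and can hide both the rise during infusion and any effect of AAT. If infused AAT in the tube alters in-tube formation, it adds a between-arm difference that did not arise in the patient. Either an absent or a present difference in TAT would then be hard to read.

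At stake is a mechanistic readout of the first dose, which section 6.1.2 places roughly 6 to 8 hours before islet infusion. Section 8.3 presents the trial as proof of concept, with its estimates meant to inform a larger one. The primary endpoint, the sample size and safety are not touched.

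**Working it through.** **1. Does any other text correct the specimen?** Every place that names TAT, a complement fragment, serum or plasma was compared. Section 6.3.1 says serum. Section 3.5.3 names the analytes without a specimen. Section 6.3.4 and Appendix 1 assign plasma to other assays only. Nothing overrides 6.3.1.

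**2. Is there an unlisted plasma tube?** Volumes stated in section 6.3:

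- IBMIR: 5 draws × 3 ml = 15 ml
- Cytokines: 6 draws × 5 ml = 30 ml
- DNA: 10 ml
- PBMC and plasma at 168 h: 10 + 15 = 25 ml
- MMTT: 2 tests × 8 times × 4 ml = 64 ml

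Sum: 15 + 30 + 10 + 25 + 64 = 144 ml, against the 145 ml stated in section 6.3.5. On these volumes there is no room for a second tube at the five IBMIR draws. The sum leaves out the AAT-level draws, for which no volume is given, and any baseline PBMC or plasma draw shown only in Appendix 1. It therefore supports the reading but does not prove it.

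**3. Does the argument need outside data?** For TAT, no: serum is what remains after clotting, clotting generates thrombin, and TAT is thrombin bound to antithrombin. For C5a, the parallel argument (complement activated in the tube) is an assumption. For C-peptide, this argument does not apply.

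**4. Would the analysis remove it?** The model in section 8.12 adjusts for a baseline value. Each tube clots separately, so one tube's in-tube formation does not cancel another's. The pre-drug tube also holds no infused AAT, whereas later tubes in the active arm may. Any drug effect in the tube would remain after baseline adjustment.

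**5. Illustration of the noise component.** The plan's figure is 80% power for 0.9 SD with up to 10% loss (section 8.3). With 32 × 0.9 = 28.8 and 16 × 0.9 = 14.4 patients and two-sided 0.05 (assumed; section 8.3 states no alpha), the standard error is √(1/28.8 + 1/14.4) = 0.323 SD. The normal approximation gives z = 0.9/0.323 − 1.96 = 0.83, so power is 0.80. The t-test gives 0.78. The plan's figure is reproduced.

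If in-tube formation adds independent variance equal to r times the true between-patient variance, the effect becomes 0.9/√(1 + r):

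| r (assumed) | effect, SD | power (t-test) |
|---|---|---|
| 0 | 0.90 | 0.78 |
| 0.5 | 0.73 | 0.60 |
| 1 | 0.64 | 0.49 |
| 2 | 0.52 | 0.35 |
| 4 | 0.40 | 0.23 |
| 9 | 0.28 | 0.14 |

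The documents give no value of r. The table shows sensitivity, not an estimate, and covers noise only, not a between-arm shift.

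**6. Schedule against text.** Sections 3.5.3 and 6.3.1 name C5a; Appendix 1 names C3a. Section 6.3.1 has three draws around the infusion (before, middle, after) and one 3 h after islet infusion. The Appendix 1 footnotes have two (0 and 15 minutes) and one 3 h after initiation. Including the pre-drug draw, 6.3.1 gives five samples and Appendix 1 four.

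**The case against.** **Serum may be loose wording.** The contents list refers to plasma levels of AAT, while section 6.2 and Appendix 1 refer to serum AAT, so the two terms are not always kept apart. This stands as a reason to confirm which tube was drawn before judging any stored sample. It does not remove the problem, because the only written instruction is serum and plasma is named separately when it is wanted.

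**The size is unknown.** This stands. A reader might infer that serum TAT mostly reflects the tube, or that it can show nothing. The documents support only that the two sources are mixed and cannot be separated afterwards.

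**The rest of the mechanistic evidence survives.** This also stands. C-peptide is one of the three IBMIR measures and is not affected, and section 3.5.3 adds a separate panel of cytokines and chemokines. A reader might infer that a null IBMIR result would be uninterpretable as a whole; that goes too far.

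**Appendix 1 can be over-read.** A reader might infer that it puts the pre-drug sample at Screening. The extracted row also puts the samples taken during and after islet infusion under the before-surgery column, where they cannot belong, so a shifted table cell is the likely cause and not an error in the plan. A reader might also infer that Appendix 1 would produce no C5a results. It is one label in a schedule; both operative sections name C5a, and samples are frozen for later assay. What remains is a conflict in wording.

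**Conclusion.** The point holds for TAT. Followed as written, section 6.3.1 yields a TAT value that combines complex formed in the tube with complex formed in the patient, and so cannot reliably show the reaction during islet infusion. It applies to every TAT draw, up to 5 × 48 = 240, but that counts tubes and does not measure the harm.

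The size of the artefact cannot be computed from the documents; the power loss shown rests on assumed variance ratios. A between-arm artefact is possible, given the stated action of AAT on thrombin and complement, but its direction and size are unknown. The C5a concern is plausible and remains an assumption.

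The endpoint is exploratory, and no primary or safety conclusion depends on it. The change should be made because it is cheap and the data are meant to inform a later trial. The mismatches in complement fragment and sampling times are real but secondary.

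**What to change.** In section 6.3.1, collect the IBMIR draws for TAT and the complement marker into an anticoagulant tube suited to the chosen assays. State the tube type and the time to centrifugation, and separate the plasma promptly. Serum may be kept for C-peptide if wanted.

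Cost: if the existing 3 ml draw is used, no extra blood. If a separate 3 ml tube is added at each of the five draws, that is 5 × 3 = 15 ml more. The itemised total rises from 144 to 159 ml, and the 145 ml in section 6.3.5 becomes about 160 ml. No visits are added.

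For samples already stored, confirm the tube used. Report TAT from samples confirmed to be serum as not reliable for thrombin formation in the patient.

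Separately, reconcile Appendix 1 and its footnotes with sections 3.5.3 and 6.3.1 on the complement fragment (C3a or C5a), the number of draws around the infusion, and whether the 3 h sample is counted from the start or the end of islet infusion. This is a text correction to one row and its footnotes.

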6.3.6. Mixed meal tolerance test (MMTT)

MMTT tests will be performed at 75±14 and 365±14 days post-surgery. During the MMTT, patients will be asked to drink a special drink called 'BOOST', which will be given at a dose of 6 mL per kilogram body weight and contains a mixture of protein, fat and carbohydrates. Patient's blood will be drawn at 0, 15, 30, 60, 90, 120, 180 and 240 min after drinking the boost. In each time point, 4ml of blood will be collected, 2ml for measuring blood glucose, and 2ml to measure c-peptide levels. Samples will be sent to the blood lab for analysis.

6.3.7. Safety laboratory tests:

Laboratory tests will be performed before hospital discharge. These are standard of care tests done in all TP-IAT patients.

6.3.6. Vital signs: Blood pressure and heart rate will be measured before hospital discharge.

6.4. FOLLOW-UP VISITS:

Autologous islet transplant recipients will be followed up life-long in our center. For this study specifically, patients will be followed up till 12 months post-transplantation. They will have to attend 2 follow-up visits scheduled on day 75 ± 14 and 365 ± 14 days after the transplant, this can be combined with their routine returning visits.

6.4.1. Mixed meal tolerance test (MMTT)

MMTT tests will be performed at 75 ± 14 and 365 ± 14 days post-surgery.

7. SAFETY MONITORING

7.1. DEFINITIONS:

7.1.1. Definition of Adverse Events (AEs)

According to the International Conference on Harmonization (ICH) Guidelines (Federal Register.1999;60(40):11285), an AE is defined as follows: An AE is any untoward medical occurrence in a subject administered an investigational drug that does not necessarily have a causal relationship with the treatment. An AE can therefore be any unfavorable and unintended sign (including an abnormal laboratory finding), symptom, or disease temporally associated with the use of the investigational product whether or not related to the investigational product. An AE is any sign, symptom, or diagnosis that appears or changes in intensity during the course of the study. An AE may be an intercurrent illness or an injury that impairs the well-being of the subject.

Unchanged chronic conditions or those related to the underlying disease or medical conditions that are consistent with natural disease progression are not AEs and should not be recorded on the AE pages of the case report form. These medical conditions should be adequately documented on the appropriate page of the form (medical history or physical examination). However, medical conditions present on the first day of treatment that worsen in intensity or frequency during the treatment or post-treatment periods should be reported and recorded as AEs. The Investigator will actively solicit this information from the subject and assess the event in terms of severity and relationship to the study treatment regimen.

7.1.2. Definition of Serious Adverse Events (SAEs)

An AE occurring with any study treatment regimen should be classified as “Serious” if it meets one of the following criteria:

- It results in death (i.e., the AE caused or led to death).
- It is life threatening (i.e., the AE placed the subject at immediate risk of death). This classification does not apply to an AE that hypothetically might cause death if it is more severe.

- It requires or prolongs inpatient hospitalization (i.e., the AE requires at least a 24 hour inpatient hospitalization or prolongs a hospitalization beyond the expected length of stay). Hospitalizations for elective medical or surgical procedures, scheduled treatments, or routine checkups are not SAEs by this criterion.
- It is disabling or incapacitating (i.e., the AE results in a substantial disruption of the subject's ability to carry out normal life functions).
- It is a congenital anomaly or birth defect (i.e., an adverse outcome in a child or fetus of a subject exposed to the molecule or study treatment regimen before conception or during pregnancy).
- It does not meet any of the above criteria, but could jeopardize the subject and might require medical or surgical intervention to prevent one of the outcomes listed above.

7.1.3. Evaluation of Adverse Events

Serious AEs should be graded with respect to severity on the following 3 point scale and reported, in detail, on the appropriate CRF page:

Grade 1: Mild AE. Discomfort noticed, but no disruption of normal daily activities; event usually requires no intervention.

Grade 2: Moderate AE: Discomfort sufficient to reduce or affect normal daily activities; even may require intervention.

Grade 3: Severe and undesirable AE: Incapacitating, with inability to perform normal daily activities; event usually requires treatment or other intervention. Subject may not be able to continue in the study.

Grade 4: Life-threatening or disabling AE

Grade 5: Death

The Investigator should evaluate the relationship of each SAE to the study treatment regimen, using the following criteria:

- **Unrelated:** Another cause of the SAE is more plausible; a clinically plausible temporal sequence is inconsistent with the onset of the AE and administration of the study treatment regimen; or a causal relationship is considered biologically impossible.
- **Possibly related:** There is a clinically plausible time sequence between onset of the SAE and administration of the study treatment regimen, but the SAE could also be attributed to concurrent or underlying disease, or the use of other drugs or procedures. "Possibly Related" should be used when the study treatment regimen is one of several biologically plausible SAE causes.
- **Definitely Related:** The SAE is clearly related to use of the study treatment regimen.

